## 7.2 NULL AND ALTERNATIVE HYPOTHESES

The analyses in this trial are descriptive and exploratory. No formal statistical test will be performed.

## 7.3 PLANNED ANALYSES

### 7.3.1 General considerations

For the determination of the MTD, only MTD evaluable patients will be considered. For the analysis of secondary and further endpoints, all patients in the treated set (i.e. patients treated with at least one dose of trial medication) will be included in the analysis. Any other analysis sets will be defined in the TSAP.

### 7.3.2 Primary endpoint analyses

In order to identify the MTD, the number of evaluable patients with DLTs during the MTD evaluation period at each dose level must be presented. Replaced patients will be excluded from the determination of MTD.

The main analysis of the MTD will use the BLRM model described above using DLT data from the MTD evaluation period.

For the analysis of tolerability and safety, please refer to [Section 7.3.5](#).

### 7.3.3 Secondary endpoint analyses

The number of patients with DLTs at each dose level during the on-treatment period will be analyzed descriptively in terms of a frequency table.

The number of patients with CTCAE Grade  $\geq 3$  treatment-related adverse events observed during the on-treatment period will be analyzed descriptively in terms of a frequency table. The number of patients with treatment related adverse events at each dose level will be analyzed descriptively in terms of a frequency table.

### 7.3.5 Safety analyses

Adverse events will be coded using the Medical Dictionary for Drug Regulatory Activities (MedDRA). Standard BI summary tables and listings will be produced. All adverse events with an onset between start of treatment and end of the residual effect period (REP), a period of 30 days after the last dose of trial medication, will be assigned to the on-treatment period for evaluation.

All treated patients will be included in the safety analysis. In general, safety analyses will be descriptive in nature and will be based on BI standards. No hypothesis testing is planned.

Statistical analysis and reporting of adverse events will concentrate on treatment-emergent adverse events, i.e. all adverse events occurring between start of treatment and end of the REP ([Section 1.2](#)) Adverse events that start before first drug intake and deteriorate under treatment will also be considered as 'treatment-emergent'.

Frequency, severity, and causal relationship of adverse events will be tabulated by system organ class and preferred term after coding according to the current version of the MedDRA at database lock.

Laboratory data will be analyzed both quantitatively as well as qualitatively. The latter will be done via comparison of laboratory data to their reference ranges. Values outside the reference range as well as values defined as clinically relevant will be summarised. Treatment groups will be compared descriptively with regard to distribution parameters as well as with regard to frequency and percentage of patients with abnormal values or clinically relevant abnormal values.

Vital signs, physical examinations, or other safety-relevant data observed at screening, baseline, during the course of the trial and at the end-of-trial evaluation will be assessed with regard to possible changes compared to findings before start of treatment.

Other safety analyses (AESIs, centrally evaluated ECG, etc.) will be specified in detail in the TSAP.

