4. CHANGES IN THE PLANNED ANALYSIS OF THE STUDY

This section is not applicable.

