6. GENERAL ANALYSIS DEFINITIONS

6.1 TREATMENT

The trial is an open-label phase I trial with dose escalation, confirmation and expansion of BI 3011441 as monotherapy. For basic study information such as treatments to be administered, assignment of treatment groups, and selection of doses, see CTP Section 4.

For safety analyses, AEs will be classified to one of the following time periods: “Screening”, “On-treatment” or “Follow-up.” This will be applied for all adverse events. Detailed rule for assigning AEs to these time periods are listed below.

- If the date of informed consent \leq AE onset date $<$ date/time of first administration of trial treatment, then the AE is assigned to “Screening”;
- If date of first administration of trial treatment \leq AE onset date \leq date of last administration of trial treatment + 30 days of Residual Effect Period (REP), then the AE is assigned to “On-treatment”;
- If AE onset date $>$ date of last administration of trial treatment + 30 days, then the AE is assigned to “Follow-up”

Table 6.1: 1 Definition of analysis treatment periods for safety analysis

Analysing Treatment Period	Start Date	Stop Date
Screening	Date of informed consent	Date/Time of the first administration of trial treatment
On-treatment	Date of the first administration of trial treatment	Date of the last administration of trial treatment + 30 days of REP
Follow-up	Date of the last administration of trial treatment + 31 days	Date of the last visit
MTD evaluation period*	Date of the first administration of trial treatment	Date of the first administration of trial treatment + 28 days (i.e., treatment cycle)

*The MTD evaluation period is only applied to the patients in the dose escalation part of the trial.

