7.5.2 Secondary endpoints

The number of patients with DLTs during the on-treatment period at each dose level will be summarized in a frequency table.

The number of patients with CTCAE Grade ≥ 3 treatment-related adverse events observed during the on-treatment period at each dose level will be summarized in a frequency table (provided tables should be refer to [Section 7.8.1.2](#)).

The number of patients with treatment related adverse events at each dose level will be summarized in a frequency table.

The secondary PK endpoints (refer to [Section 5.2.2](#)) will be analysed descriptively. The analysis of standard PK parameters is calculated according to the relevant BI internal procedures “Noncompartmental Pharmacokinetic / Pharmacodynamic Analyses of Clinical Studies” (6).

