7.8.1 Adverse Events

Statistical analysis and reporting of adverse events will concentrate on treatment-emergent adverse events, i.e., all adverse events occurring between start of treatment and end of the REP. All adverse events will be evaluated by initial treatment.

Frequency, severity, and causal relationship of adverse events will be tabulated by system organ class and preferred term after coding according to the current version of the Medical Dictionary for Drug Regulatory Activities (MedDRA) at database lock.

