7.8.1.2 Adverse events

Unless otherwise specified, the analyses of AEs will be descriptive in nature. All analyses of AEs will be based on the number of patients with AEs and NOT on the number of AEs. The analysis will be based on BI standards (3). AEs will be coded using the most recent version of MedDRA. The severity of AEs will be assessed according to the Common Terminology Criteria for Adverse Events (CTCAE) Version 5.0.

For analysis multiple AE occurrence data on the eCRF will be collapsed into an AE provided that all of the following applies:

- All AE attributes are identical (Low Level term [LLT], severity, action taken, therapy required, seriousness, reason for seriousness, relationship, outcome, AESI).
- The occurrences were time-overlapping or time-adjacent (time-adjacency of 2 occurrences is given if the second occurrence started on the same day or on the day after the end of the first occurrence).

The analysis of AEs will be based on the concept of treatment emergent AEs. That means that all AEs occurring between first drug intake until 30 days of REP after last drug intake will be assigned to 'on-treatment'. All AEs occurring before first drug intake will be assigned to 'screening' and all AEs occurring after last drug intake + 30 days will be assigned to 'follow-up' (for listings only). For details on the treatment definition, see [Section 6.1](#).

The pre-specified Adverse events of special interest (AESIs) in this trial are DLTs and lab abnormalities in hepatic laboratory parameters. Refer to CTP Section 5.2.6.1.4 for details.

An overall summary of adverse events will be presented.

The frequency of patients with AEs will be summarized by treatment, primary system organ class (SOC) and/or preferred term (PT). The SOCs will be sorted by default alphabetically and PTs will be sorted by frequency within an SOC. Separated tables will be provided for patients with

- AEs
- Drug-related SAEs
- Drug-related AEs
- SAEs
- AESIs
- Grouped term AEs
- AEs leading to death
- AEs leading to discontinuation of trial medication

- AEs leading to dose interruption
- AEs leading to dose reduction
- DLTs during the MTD evaluation period
- DLTs during the entire treatment period

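### The SAP omits the protocol's rule that adverse events starting before dosing and worsening on drug are treatment-emergent; whether any event is lost depends on how worsening is recorded

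*Protocol*

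**What the plan says.** Protocol 7.3.5 has two rules. The first assigns events to the on-treatment period by onset: "All adverse events with an onset between start of treatment and end of the residual effect period (REP". The residual effect period lasts 30 days from the final dose. The second widens the treatment-emergent definition: "Adverse events that start before first drug intake and deteriorate under treatment will also be considered as" treatment-emergent.

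The SAP keeps only the first idea:

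- Section 6.1 compares the onset date with dosing. If onset is on or after consent but before "date/time of first administration of trial treatment, then the AE is assigned to" Screening. On scope it says: "This will be applied for all adverse events".
- Section 7.8.1 limits reporting to "treatment-emergent adverse events, i.e., all adverse events occurring between start of treatment and end of the REP". The protocol's next sentence, on deterioration, is missing.
- Section 7.8.1.2 repeats the rule: "All AEs occurring before first drug intake will be assigned to" the screening period.
- Section 4, on changes to the planned analysis, reads: "This section is not applicable".

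The period assignment feeds a secondary endpoint. SAP 7.5.2 provides that Grade 3 or higher "treatment-related adverse events observed during the on-treatment period at each dose level will be summarized in a frequency table".

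**The concern.** The two documents can classify the same event differently, and the SAP does not declare the difference. The case in question is an AE that begins between consent and first dose and becomes more severe on drug.

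Such events can exist in the database. Protocol 5.2.6.2.1 collects AEs from informed consent, and the flow chart allows up to 28 days of screening. Inclusion criterion 11 admits patients with residual Grade 1 toxicity from earlier therapy, and with stable sensory neuropathy up to Grade 2.

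If an event of this kind is held in the Screening period, the error can go only one way, towards less apparent toxicity, in a trial whose primary objective is safety and tolerability. For laboratory values the SAP follows worsening through shift tables from baseline to worst value (7.8.2). It describes no equivalent for clinical AEs.

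**Working it through.** There is no figure in the plan to reproduce. Protocol 7.2 plans no formal test and 7.6 makes no power calculation, so nothing numerical rests on this definition. The check applies both sets of rules to three test cases.

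| Case | Protocol 7.3.5 | SAP 6.1, 7.8.1, 7.8.1.2 |
|---|---|---|
| A. Onset between consent and first dose, one record, Grade 1 rising to Grade 3 after first dose | Treatment-emergent, by the deterioration rule | Screening, by onset date |
| B. Same course, but the worsening is a second occurrence with a post-dose start date | On-treatment, by onset | On-treatment, by onset |
| C. Condition present before consent; its worsening on drug is recorded as an AE (Protocol 5.2.6.1.1) | On-treatment, by onset of the worsening | On-treatment, by onset of the worsening |

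**Case A** is the only one in which the documents disagree. Under the SAP the event is absent from the treatment-emergent tables. If it was judged related, it is also absent from the Grade 3 or higher count in 7.5.2.

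**Case B** survives the SAP's data handling. Section 7.8.1.2 merges occurrences only when all listed attributes agree, and severity is one of them. A Grade 1 and a Grade 3 occurrence therefore stay separate, and the second keeps its own start date.

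**Which case applies?** Neither document says that a grade increase in an AE that began during screening must open a new occurrence. The collapsing rule governs occurrences that already exist and does not require one to be created. Protocol 5.2.6.1.1 says that worsening of a pre-existing condition is recorded as an AE, but gives no onset date for an AE that itself started in screening.

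**Scale, assuming exactly one affected patient:**

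- cohort of 3: 1/3 = 33.3 percentage points
- cohort of 6: 1/6 = 16.7 percentage points
- all of about 12 patients: 1/12 = 8.3 percentage points

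These show what one patient weighs. They do not estimate how many patients would be affected, and the documents offer no basis for such an estimate.

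**The case against.** Five arguments can be made for the plan.

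1. *The protocol's own on-treatment period is defined by onset.* This stands. The endpoint on Grade 3 or higher related AEs is tied to that period in both documents, and the protocol does not say how a worsened event enters it. A reader might infer that the SAP changed a clear protocol rule for the endpoint. The documents do not support that: the clear departure is in the treatment-emergent definition, and for the endpoint the SAP leaves open a question the protocol had not settled.

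2. *The text points to separate records.* This also stands in part. Protocol 5.2.6.1.1 and the collapsing rule in SAP 7.8.1.2 both fit a practice in which a grade change is its own occurrence. Neither makes it a requirement.

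3. *The affected set is narrow.* Agreed for the endpoint, which needs the event to be Grade 3 or higher and judged related. Protocol 5.2.6.1.6 lists pre-treatment cases among the arguments against causality, so an investigator who attributes a worsening to the drug has reason to record it as new. The treatment-emergent tables of all AEs have no relatedness condition and remain exposed.

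4. *The SAP assumes familiarity with the protocol, and the sponsor's AE guide may cover worsening.* The guide cannot be checked here. Silence might be filled from the protocol, but SAP 6.1 is not silent: it gives a rule and applies it to all AEs.

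5. *The MTD is protected.* Largely agreed. Dose-limiting toxicities (DLTs) are reported within 24 hours as AEs of special interest and reviewed by the Safety Monitoring Committee (Protocol 5.2.6.1.4 and 5.2.6.3).

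**Conclusion.** The SAP states a classification rule that conflicts with the protocol's treatment-emergent definition and does not declare the change. That much rests on the text alone.

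The consequence is conditional. Toxicity is understated only if a worsening stays on the record that carries the pre-dose onset date and, for the Grade 3 or higher endpoint, only if the event is also judged related. A reader might infer that worsened events will be lost from the safety endpoints, or that dose-level rates will be low by 17 to 33 percentage points. The documents support neither inference: separate occurrences would be counted correctly, and those percentages are simply one patient in six or in three. The number of affected events is unknown, an effect on the MTD is unlikely, and all the analyses concerned are descriptive. This is a minor point, worth correcting because the correction is easy.

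**What to change.** In SAP 6.1, 7.8.1 and 7.8.1.2:

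- Assign to the on-treatment period any AE with pre-dose onset whose CTCAE grade increases between first dose and last dose + 30 days. Use the start date of the higher-grade occurrence as its onset for this purpose.
- State that each grade increase is a separate eCRF occurrence with its own start date. Without this, the date of worsening may not be in the data.
- Where only one record exists, flag it as treatment-emergent if the recorded grade exceeds the pre-dose grade. This requires the pre-dose grade to be available.

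If the sponsor means to keep classification by onset alone, SAP Section 4 should declare the departure from Protocol 7.3.5.

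The cost is a sentence or two in three SAP sections and one derivation step, plus an eCRF completion instruction if grade changes are not already entered as separate occurrences. No design or sample-size change follows.

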### 7.3.6 Other Analyses

The pharmacokinetic parameters listed in [Section 2.1.3](#) will be calculated according to the internal BI standard operating procedure (SOP). PK analyses will be performed using validated software programs, normally, Phoenix WinNonlin (Pharsight®) with applications validated for the respective purpose. Graphs and tables will be generated using validated customised SAS® macros or appropriate graphic software.

### 7.3.7 Interim Analyses

The sponsor will continuously monitor the safety. The dose escalation design foresees that the sponsor and the SMC perform regular safety evaluations. These evaluations will be unblinded to dose.

## 7.4 HANDLING OF MISSING DATA

No imputation will be performed on missing efficacy data. Missing baseline laboratory values will be imputed with the respective values from the screening visit. No other imputations will be performed on missing data unless otherwise specified in the TSAP. Every effort will be made to obtain complete information on all adverse events, with particular emphasis on DLTs.

Handling of missing PK data will be performed according to the internal BI SOP. 

## 7.5 RANDOMISATION

No randomisation will be performed. Patients will be assigned to escalating dose groups by order of admission into the trial.

## 7.6 DETERMINATION OF SAMPLE SIZE

No formal statistical power calculations to determine sample size were performed for these parts of the trial. Approximately 12 patients (including at least 6 patients at MTD) are expected for dose escalation based on the number of dose levels/cohorts that are tested. Fewer or more patients might be needed based on the recommendation of the SMC. However, the actual number of patients will depend on the number of dose cohorts tested. Detailed information of simulation study to evaluate operating characteristics of the BLRM will be provided in [section 10.2](#).

## 8. INFORMED CONSENT, TRIAL RECORDS, DATA PROTECTION, PUBLICATION POLICY, AND ADMINISTRATIVE STRUCTURE

The trial will be carried out in accordance with the Medical Devices Directive (93/42/EEC) and the harmonised standards for Medical Devices (ISO 14155, current version).

The trial will be carried out in compliance with the protocol, the ethical principles laid down in the Declaration of Helsinki, in accordance with the ICH Harmonized Guideline for Good Clinical Practice (GCP), relevant BI Standard Operating Procedures (SOPs), the Japanese GCP regulations (Ministry of Health and Welfare Ordinance No. 28, March 27, 1997) and other relevant regulations. Investigators and site staff must adhere to these principles. Deviation from the protocol, the principles of ICH GCP or applicable regulations as will be treated as “protocol deviation”.

Standard medical care (prophylactic, diagnostic and therapeutic procedures) remains the responsibility of the treating physician of the patient.

The investigator will inform the sponsor immediately of any urgent safety measures taken to protect the trial patients against any immediate hazard, as well as of any serious breaches of the protocol or of ICH GCP.

The Boehringer Ingelheim transparency and publication policy can be found on the following web page: [trials.boehringer-ingelheim.com](http://trials.boehringer-ingelheim.com). The rights of the investigator and of the sponsor with regard to publication of the results of this trial are described in the investigator contract. As a rule, no trial results should be published prior to finalisation of the Clinical Trial Report. The certificate of insurance cover is made available to the investigator and the patients, and is stored in the ISF.

### 8.1 TRIAL APPROVAL, PATIENT INFORMATION, INFORMED CONSENT

This trial will be initiated only after all required legal documentation has been reviewed and approved by the respective Institutional Review Board (IRB) / Independent Ethics Committee (IEC) and competent authority (CA) according to national and international regulations. The same applies for the implementation of changes introduced by amendments.

Prior to patient participation in the trial, written informed consent must be obtained from each patient (or the patient's legally accepted representative) according to ICH-GCP and to the regulatory and legal requirements of the participating country. Each signature must be personally dated by each signatory and the informed consent and any additional patient-information form retained by the investigator as part of the trial records. A signed copy of the informed consent and any additional patient information must be given to each patient or the patient's legally accepted representative.”

The investigator or delegate must give a full explanation to trial patients based on the patient information form. A language understandable to the patient should be chosen, technical terms and expressions avoided, if possible.

The patient must be given sufficient time to consider participation in the trial. The investigator or delegate obtains written consent of the patient's own free will with the informed consent form after confirming that the patient understands the contents. The investigator or his delegate must sign (or place a seal on) and date the informed consent form. If a trial collaborator has given a supplementary explanation, the trial collaborator also signs (or places a seal on) and dates the informed consent.

Re-consenting may become necessary when new relevant information becomes available and should be conducted according to the sponsor's instructions.

The consent and re-consenting process should be properly documented in the source documentation.

## 8.2 DATA QUALITY ASSURANCE

A risk-based approach is used for trial quality management. It is initiated by the assessment of critical data and processes for trial subject protection and reliability of the results as well as identification and assessment of associated risks. An Integrated Quality and Risk Management Plan documents the rationale and strategies for risk management during trial conduct including monitoring approaches, vendor management and other processes focusing on areas of greatest risk.

Continuous risk review and assessment may lead to adjustments in trial conduct, trial design or monitoring approaches.

A quality assurance audit/inspection of this trial may be conducted by the sponsor, sponsor's designees, or by IRB / IEC or by regulatory authorities. The quality assurance auditor will have access to all medical records, the investigator's trial-related files and correspondence, and the informed consent documentation of this clinical trial.

## 8.3 RECORDS

CRFs for individual patients will be provided by the sponsor. For drug accountability, refer to [section 4.1.8](#).

### 8.3.1 Source documents

In accordance with regulatory requirements, the investigator should prepare and maintain adequate and accurate source documents and trial records that include all observations and other data pertinent to the investigation on each trial patient. Source data as well as reported data should follow the "ALCOA principles" and be attributable, legible, contemporaneous, original and accurate. Changes to the data should be traceable (audit trail).

Data reported on the CRF must be consistent with the source data or the discrepancies must be explained.

The current medical history of the patient may not be sufficient to confirm eligibility for the trial and the investigator may need to request previous medical histories and evidence of any diagnostic tests. In this case, the investigator must make at least one documented attempt to

retrieve previous medical records. If this fails, a verbal history from the patient, documented in their medical records, would be acceptable.

If the patient is not compliant with the protocol, any corrective action e.g. re-training must be documented in the patient file.

For the CRF, data must be derived from source documents, for example:

Patient identification: gender, year of birth (in accordance with local laws and regulations)

Patient participation in the trial (substance, trial number, patient number, date patient was informed)

Dates of patient's visits, including dispensing of trial medication

Medical history (including trial indication and concomitant diseases, if applicable)

Medication history

Adverse events and outcome events (onset date (mandatory), and end date (if available))

Serious adverse events (onset date (mandatory), and end date (if available))

Concomitant therapy (start date, changes)

Originals or copies of laboratory results and other imaging or testing results, with proper documented medical evaluation (in validated electronic format, if available)

Completion of patient's participation in the trial" (end date; in case of premature discontinuation document the reason for it).

Prior to allocation of a patient to a treatment into a clinical trial, there must be documented evidence in the source data (e.g. medical records) that the trial participant meets all inclusion criteria and does not meet any exclusion criteria. The absence of records (either medical records, verbal documented feedback of the patient or testing conducted specific for a protocol) to support inclusion/exclusion criteria does not make the patient eligible for the clinical trial.

